6.4 SUMMARY OF PRE-PROCEDURE PREPARATION

CONFIDENTIAL: Contains Proprietary Information

All eligible subjects who have signed an informed consent and are on alpha blockers or beta blockers will undergo a washout period of 2 weeks or 7 days, respectively. Subjects who have been on a stable dosing of beta blockers for the last 6 months (i.e. no dose changes) do not need to undergo the 7 day washout period.

Subjects are to be given an oral anti-anxiety medication prior to treatment. This medication must be given at least 45 minutes prior to the procedure, but no more than 2 hours before the procedure. No anesthesia will be allowed. Pain killer may be prescribed at the physician's discretion.

6.5 FOLLOW-UP

The following evaluations will be completed at the follow-ups as indicated:

Table 6-1: Evaluations at Follow Up

Follow up period	Description
1 day (1-2 days)	Check for AE
	IPSS
	Pain assessment
	Medications
1 week (4-7 days)	Check for AE
	Pain assessment
	IPSS, Subject Satisfaction Questionnaire
	Cystoscopy
	Uroflow
	MRI
1 month (3-5 weeks)	Check for AE
	Pain assessment
	Uroflow
	IPSS, BPHII, IIEF, EQ5D, MSHQ-EjD SF
	MRI
	Medications
3 months (12 – 14 weeks)	Check for AE
	Pain assessment
	Uroflow
	IPSS, BPHII, IIEF, EQ5D, MSHQ-EjD SF, Subject Satisfaction Questionnaire
	PSA
	Prostate Volume
	MRI
Medications	
6 months (24-28 weeks)	Check for AE
	Pain assessment
	Uroflow
	IPSS, BPHII, IIEF, EQ5D, MSHQ-EjD SF, Subject Satisfaction Questionnaire
	PSA

CONFIDENTIAL: Contains Proprietary Information

	Prostate Volume
	MRI
	Medications
12 months (11-13 months)	Check for AE
	Pain assessment
	Uroflow
	IPSS, BPHII, IIEF, EQ5D, MSHQ-EjD SF, Subject Satisfaction Questionnaire
	PSA
	Prostate Volume
	Medications
Annually for up to 5 years. Annual check up may be within 2 months of the anniversary of the procedure	Check for AE
	IPSS, BPHII, EQ5D, MSHQ-EjD SF, Subject Satisfaction Questionnaire
	Medications
Unscheduled	Check for AE
	Pain assessment (optional)
	Medications
	IPSS, BPHII, IIEF,MSHQ-EjD SF (all optional)
	Uroflow (optional)

6.5.1 Scheduled Follow-up Visits

Table 6-2: Schedule of Visits

	Baseline Pre-Op	1 day	1 week	1 month	3 month s	6 month s	1 year	Annual (2-5 years)	Unsched uled
IPSS	√	√	√	√	√	√	√	√	optional
BPH Impact Index	√			√	√	√	√	√	optional
EQ5D	√			√	√	√	√	√	
Sexual function (IIEF)	√			√	√	√	√	√	optional
MSHQ-EjD Short Form	√			√	√	√	√	√	optional
Subject Satisfaction Questionnaire			√	√	√	√	√	√	optional
Subject Pain Assessment		√	√	√	√	√			
Uroflow (Qmax + PVR)	√		√	√	√	√	√		optional
Urodynamics	√								
Prostate specific antigen (PSA)	√				√	√	√	√	
Prostate Volume	√				√	√	√	√	
Cystoscopy	√		√						
MRI	option al		√	√	√	√			
Adverse event(s)		√	√	√	√	√	√	√	√
Medication(s) used	√	√	√	√	√	√	√	√	√

7 ADVERSE EVENTS

7.1 DEFINITION OF ADVERSE EVENT(S)

For the purpose of this protocol, an “adverse event” (AE) will be defined as any adverse medical condition change (i.e., *de novo* or increased severity in a preexisting condition) from the subject’s baseline condition that occurs during the course of the clinical study, after starting study procedure, whether considered procedure-related or not. Therefore, conditions existing at the time of enrollment will not be reported as an AE unless the event increased in clinically significant severity during the course of the study. Events which resolve and then recur should be reported as separate AEs. Events that are a continuation of an unresolved AE should not be reported as a new AE but a continuation of the previously reported AE.

The reason for catheterization will not be considered an AE if catheterization occurs and ends within 72 hours after the procedure because this is generally considered standard of care to allow the tissue to heal.

The reason for catheterization will be considered an adverse event if the following applies:

- a. If catheterization occurs within a 72-hour window after the procedure and the duration of catheterization extends beyond that 72-hour window
- b. If catheterization occurs outside of a 72-hour window after the procedure
- c. If catheterization recurs after the same symptom is resolved

Lower Urinary Tract Symptoms (LUTS) will not be considered an adverse event if LUTS occurs and ends within a 3-day window (72 hours) after the procedure.

Lower Urinary Tract Symptoms (LUTS) will be considered an adverse event if the following applies:

- a. If LUTS occurs within a 3-day window (72 hours) after the procedure and the duration of LUTS extends beyond that 3-day window (72 hours)
- b. If LUTS occurs outside of a 3-day window (72 hours) after the procedure
- c. If LUTS recurs after the same symptom is resolved

Normally expected symptoms caused by the treatment will not be considered AEs for this study. For example, normal pain or minor bruising at the surgical site due to the healing of the site will not be considered an AE. “Treatment” includes all procedures and treatments administered according this protocol.

An AE may be volunteered spontaneously by the subject or discovered as a result of questioning or by physical examination by the investigator.

AEs should be classified according to their underlying cause, if known, (e.g., fever resulting from infection should be reported as “infection”). Concomitant AEs that are unrelated (in the clinician’s judgment) should be reported as separate events.

AE determination is based on three levels of evidence:

Level 1 – final diagnosis

Level 2 – signs

Level 3 – symptoms

Every effort should be made to collect Level 1 evidence of any AE. If an AE has all three levels of evidence, an AE should be reported only once at the highest level of severity, which is the final diagnosis (Level 1). A single AE should not be reported as multiple AEs based on separate symptoms, signs, and diagnosis.

In cases where a diagnosis is not possible, AE determination should be based on the next highest level of evidence (signs, Level 2), followed by symptoms (Level 3), if only symptoms are available.

A corrective action itself is not an AE. The AE should always be determined based on the reason that a corrective action was taken.

Note: there may be multiple symptoms representing or associated with only one AE. In this case only one AE should be reported. The symptoms can be captured within the AE description. If the symptoms are related to LUTS, complete the LUTS form in addition to the AE form. If AE requires catheterization, then complete the catheterization form.

Figure 7-1 is an AE determination and outcome flowchart.

[figure not shown]

Figure 7-1: AE Determination and Outcome Flowchart

Examples

Subject is diagnosed with urinary retention and requires catheterization for more than 3 days. In addition, they have symptoms of irritation, urgency, and hematuria. Only one AE – retention should be reported. The additional symptoms should be noted in the AE description. Catheterization is the treatment.

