5.3.2 Endpoint 2: Post-Procedure Catheterization

All subjects will be kept at the clinic for observation for 24 hours post-procedure. Post procedure catheterization will only be allowed if the Principal Investigator determines that

the subject has symptoms of retention (defined as failure to void within 8 hours post procedure) or requires catheterization for other safety reasons.

5.3.3 Endpoint 3: Lesion size, as measured by MRI at Week 1 post-procedure.

5.3.4 Endpoint 4: Change in IPSS score from baseline at various points post-procedure.

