7.2 STUDY RELATED AE DEFINITION

This section applies particularly to the Phase 2 part of the study. The transurethral intervention with a rigid scope similar in size to the Rezūm device commonly is associated with transient symptoms. For the purpose of this study, these types of transient symptoms will not be considered an adverse event. The corollary to a surgical procedure is bleeding. Bleeding will occur in all surgical BPH procedures, and bleeding, therefore, is not clinically significant and typically not reported as an AE. The following types of signs and symptoms that are attributed to the procedure, last less than or equal to 72 hours, AND do not result in intervention, re-hospitalization, or prolonged unplanned hospitalization, will not be considered AEs.

- Dysuria
- Hematuria
- Storage (irritative) LUTS
- Urgency/frequency
- Nocturia
- Urge incontinence
- Voiding (obstructive) LUTS
- Hesitancy
- Decrease flow
- Increase residual
- Pain/discomfort
- Catheterization

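### Sections 7.1 and 7.2 exempt early catheterization and LUTS from the Phase 2 AE count on different conditions, and no text shown says which section governs

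*Combined protocol and SAP*

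**What the plan says.** All references are to the combined protocol and SAP.

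- **Section 7.1, catheterization.** The reason for a catheter is not an AE when "catheterization occurs and ends within 72 hours after the procedure because this is generally considered standard of care to allow the tissue to heal". It is an AE under (a), "If catheterization occurs within a 72-hour window after the procedure and the duration of catheterization extends beyond that 72-hour window"; under (b), when the catheter starts after the window; and under (c), when catheterization recurs after the symptom has resolved.
- **Section 7.1, other exemptions.** LUTS "will not be considered an adverse event if LUTS occurs and ends within a 3-day window (72 hours) after the procedure". More broadly, "Normally expected symptoms caused by the treatment will not be considered AEs for this study".
- **Section 7.1, notes and example.** The AE is the reason for a corrective action, not the action. The catheterization form is requested when an AE requires a catheter. The worked example reports retention as one AE when the catheter is needed for more than 3 days, and it calls catheterization the treatment.
- **Section 7.2.** "This section applies particularly to the Phase 2 part of the study". Listed signs and symptoms attributed to the procedure that "last less than or equal to 72 hours, AND do not result in intervention, re-hospitalization, or prolonged unplanned hospitalization, will not be considered AEs". The list includes obstructive voiding LUTS and catheterization. Retention is not listed by name.
- **Section 5.3.2 (Endpoint 2).** A catheter is permitted on two grounds only, as judged by the investigator: "the subject has symptoms of retention (defined as failure to void within 8 hours post procedure) or requires catheterization for other safety reasons". A 24-hour observation stay is planned for every subject.
- **Sections 7.4, 7.6 and 14.2.** Seriousness is assessed on an AE, and prolonged hospitalization is one of the criteria. The AE CRF records intensity and relationship to the device. AEs are summarized descriptively by frequency, severity and relationship.

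**The concern.** Two adjoining sections define what is not an AE, and they use different tests. Section 7.1 asks only when the first catheter, or the LUTS, began and ended relative to the procedure. Section 7.2 asks how long the event lasted, whether the procedure caused it, and whether it led to an intervention or more hospital time. Nothing in the shown text says which test prevails in Phase 2.

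Phase 2 is meant to add to the safety record (section 5.1), and adverse responses are collected for all treatment settings (section 5.2). AE status decides whether an event receives an intensity grade and a device-relationship rating, and whether it can be assessed as serious. If 7.1 is followed literally, an early retention that lengthens the hospital stay has no route into the SAE listing.

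The form instruction adds a smaller problem. Catheterization is an endpoint, yet the note in 7.1 asks for its form only when the catheter was required by an AE.

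**Working it through.** The plan gives no retention rate, catheterization rate or sample-size calculation, so there is no figure to reproduce. The check applies both rules to the same events.

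**Rules.** Let s and e be the hours after the procedure at which the catheter starts and ends.

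- 7.1: not an AE if it is the first catheter, s ≤ 72 and e ≤ 72; otherwise its reason is an AE.
- 7.2: exempt if attributed to the procedure, e − s ≤ 72, and there is no intervention, readmission or unplanned longer stay.

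Section 7.2 does not define an intervention, so it can be read in two ways. On reading L the catheter is itself a listed, exempt item. On reading I the catheter is the disqualifying intervention. The start and end hours below are illustrative, except that hour 8 is when the retention definition in 5.3.2 is first met. All events are taken as attributed to the procedure.

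| Event | 7.1 | 7.2, reading L | 7.2, reading I |
|---|---|---|---|
| First catheter, hours 8–40, uncomplicated | not AE | exempt | not exempt |
| Same, with unplanned longer stay | not AE | not exempt | not exempt |
| First catheter, hours 60–90 | AE (a) | exempt (30 h) | not exempt |
| Catheter, hours 120–144 | AE (b) | exempt (24 h) | not exempt |
| Recurrent catheter, hours 30–50 | AE (c) | exempt (20 h) | not exempt |
| First catheter, hours 8–90 | AE (a) | not exempt (82 h) | not exempt |

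**Row 2** conflicts on both readings. Failing the 7.2 exemption matters because 7.1 opens by making any adverse change from baseline an AE; an event that no exemption covers defaults to AE. Here 7.1 exempts and 7.2 does not, and no order of precedence is stated. The planned 24-hour stay would not trigger the condition by itself, because it is planned. The same conflict arises for early LUTS, since 7.1's LUTS exemption also lacks the hospitalization condition, and for an early catheter not attributed to the procedure.

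**Rows 3 to 5** conflict only on reading L. For a first catheter with s ≤ 72, 7.1's window closes at hour 72 and 7.2's limit at hour s + 72. The rules therefore disagree for removal after hour 72 and up to hour s + 72, a span of s hours:

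- s = 8: up to hour 8 + 72 = 80
- s = 24: up to hour 24 + 72 = 96
- s = 60: up to hour 60 + 72 = 132

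The catheter at hours 60–90 lasts 90 − 60 = 30 h. It ends 90 − 72 = 18 h past the 7.1 window and is 72 − 30 = 42 h inside the 7.2 limit.

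**Row 1** conflicts only on reading I. The two time rules cannot disagree in this row: a catheter that starts and ends within 72 h of the procedure lasts no more than 72 h.

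**Size.** Phase 2 enrolls up to 15 subjects, so one reclassified subject moves the frequency by 1/15 = 6.7 points. For assumed counts of 1, 3 and 5 disputed subjects, the choice is between 0% and 6.7%, 20.0% or 33.3%. These counts only show scale; the documents support no particular number.

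**The case against.** A reader might infer that the retention AE count is undefined for any early catheter. The documents do not support that. For a first catheter that starts and ends within 72 hours, 7.1 says outright that its reason is not an AE. Section 7.2 never says that it is one, and it lists catheterization among the exempt items. If every catheter were a disqualifying intervention, that list entry could never operate. The 7.1 example, with a catheter for more than 3 days, fits the same 72-hour convention. Figure 7-1, the AE determination flowchart, is not shown and may settle the order. This case is ambiguous on one reading of 7.2, because an intervention is undefined and the 7.1 example calls catheterization the treatment.

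Nor can the row 1 and row 3 conflicts be added together. They rest on opposite readings of 7.2, and only one can be right.

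Other inferences also fail. Naming retention as an anticipated event in 7.3 is not a counting rule; 7.3 also names pain, dysuria and urgency, which 7.2 exempts when brief. The standard-of-care rationale in 7.1 sits poorly with the restrictive wording of 5.3.2, but that is a criticism of the reason, and the rule still operates. The events are not lost either: catheterization is Endpoint 2, and section 5.2 collects catheterization requirements and short-term obstructive symptoms whatever their AE status.

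The study is single-arm, single-center and descriptive, and no decision rule uses the retention AE count. All of this stands and limits the weight of the point. It does not answer row 2, which depends on neither reading of intervention. Letting 7.1 always prevail would also leave 7.2's extra conditions with no work to do for first catheters and LUTS confined to the 72-hour window.

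**Conclusion.** The two sections state different exemption rules for early catheterization and LUTS, and they need to be reconciled.

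- The firmest conflict is the early event that prolongs hospitalization: a non-AE under 7.1, so outside the test in 7.4, but not exempt under 7.2.
- The window-versus-duration mismatch is real if the catheter is treated as a listed 7.2 item.
- The uncomplicated early catheter has a definite answer in 7.1 and is ambiguous, not undefined, when 7.2 is read beside it.
- The form instruction leaves it unclear whether the form is needed for a non-AE catheter, although start and stop times are what either time rule needs.

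Each reclassified subject is worth 6.7 points at N = 15, and more if fewer are enrolled. The number affected cannot be estimated. The conclusion assumes that Figure 7-1 does not state which section governs. It concerns the classification and reporting of AEs; Endpoint 2 itself is intact.

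**What to change.** 1. Reconcile 7.1 and 7.2 for Phase 2, and check Figure 7-1 against the result. State one time rule, either a window from the procedure or a duration, and say which section governs.
2. Apply 7.2's attribution and hospitalization conditions to 7.1's catheterization and LUTS exemptions too, and align the general exemption for expected symptoms with them.
3. State whether an intervention includes or excludes the catheterization listed in 7.2, and whether retention falls under obstructive voiding LUTS.
4. Complete the catheterization form, with start and stop times, for every therapeutic catheter whatever its AE status. In/out catheterization to measure PVR (section 14.8.9) is not meant.
5. In 14.2, report retention and catheterization that start and end within 72 hours of the procedure on a separate descriptive line. A listing by treatment setting is optional, because at most 15 subjects spread over adjustable settings would give sparse cells.

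The cost is protocol wording, one form instruction and one table line. The reported AE rate may rise, by 6.7 points per reclassified subject at N = 15; the separate line keeps brief events distinguishable. Care of subjects does not change.

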5.2 STUDY DESIGN

In this Phase 2 study, up to 15 subjects with LUTS secondary to BPH requiring surgical treatment will be treated with the Rezūm System. Treatment is ≤ 10 seconds per treatment. The power and water flow rate settings may be adjusted slightly to minimize pain and swelling to the subjects while maximizing the treatment area (e.g., lesion size). The power setting will be between 175W and 250W with a concomitant adjustment to the water flow rate of 2.7 ml/min to 5.0 ml/min. The actual power output will be recorded. For all the treatment settings, adverse and subject responses will be collected. The range of acceptable power setting have been determined in bench-top, animal studies, testing on extirpated human prostate to create lesions of a size that is adequate to treat the BPH tissue. The unknown factor that will be evaluated in this Phase 2 study is the acute response(s) to the different treatments in terms of procedural and post procedural discomfort. If the subjects are able to tolerate the higher caloric treatments, those treatments will be used in subsequent subjects. If the subjects are not able to tolerate a particular caloric treatment, the lower caloric treatment will be used in subsequent subjects.

The standard Rezūm treatment following the IFU will be followed. Information regarding the vapor needle configuration, treatment settings, treatment medications, pain or discomfort during treatment, post-treatment catheterization requirements, and the type and severity of any short term irritative or urinary obstructive symptoms will be collected. Information regarding the subjects' symptomatic response and uroflowmetry characteristics will be collected at baseline and in follow-up evaluations conducted with each subject. Any adverse events will be evaluated at each visit. Lesion characteristics and treated tissue resorption rate will be measured by gadolinium enhanced MRI imaging techniques performed post-procedure at specified intervals.

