5.4 INCLUSION CRITERIA

- 1. Male subjects \geq 45 years of age who have symptomatic / obstructive symptoms secondary to BPH requiring invasive intervention.**
- 2. IPSS score of \geq 15.**
- 3. Qmax: Peak flow rate \leq 15 ml/sec.**
- 4. Post-void residual (PVR) $<$ 300 ml.**
- 5. Prostate transverse diameter $>$ 30 mm.**
- 6. Prostate volume between 20 to 120 gm.**
- 7. Voided volume \geq 125 ml.**
- 8. Subject able to complete the study protocol in the opinion of the Principal Investigator.**
- 9. Subject must be willing to undergo the procedure without anesthesia.**

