14.8.1 IPSS¹

The IPSS is a standardized, validated, and reliable self-administered questionnaire that utilizes 7 questions to assess the frequency and severity of a subject's obstructive and irritative symptoms, with each question scored on a scale of 0 (not at all) to 5 (almost always). Total scores on the IPSS can range from 0-35; a score of 7 or less represents subjects with mild symptoms; 8-19 represents those with moderate symptoms; and subjects with scores from 20-35 typically have severe symptoms.

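### Section 7.1 does not say whether its LUTS rules (a)-(c) or its baseline-referenced AE definition prevails, so residual or returning BPH symptoms may or may not be counted as AEs

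*Combined protocol and SAP*

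**What the plan says.** All three elements are in the combined protocol and SAP.

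- **General definition (7.1, opening paragraph).** An AE is a new condition or a worsening from the subject's baseline. The text adds that "conditions existing at the time of enrollment will not be reported as an AE unless the event increased in clinically significant severity".
- **LUTS rules (7.1, later).** LUTS that begins and ends within 72 hours of the procedure is not an AE. LUTS is an AE if it starts within that window and outlasts it (rule a); "If LUTS occurs outside of a 3-day window (72 hours) after the procedure" (rule b); or "If LUTS recurs after the same symptom is resolved" (rule c). None of the three mentions baseline, and (b) and (c) have no end date.
- **Population (5.2, 5.4).** Phase 2 treats "up to 15 subjects with LUTS secondary to BPH requiring surgical treatment", and entry requires an IPSS of at least 15.

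AEs are checked at every visit up to 5 years (6.5). Section 14.2 reports them by frequency, severity and relationship to the device.

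**The concern.** LUTS is the condition being treated, so every Phase 2 subject has it before the procedure. A rule that makes LUTS an AE on timing alone can then record three different things under one term: a new irritative or obstructive problem, disease that has improved but not gone, and BPH that has come back. The opening definition would keep only the first, together with true worsening. If sites or monitors differ on which text governs, identical histories give different AE counts.

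The analysis is descriptive, and one of the two Phase 2 objectives in 5.1 is to document safety and post-operative effects. The AE frequencies are therefore a main part of the safety result, with no test or comparator behind them. The LUTS line needs a single meaning.

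**Working it through.** The plan states no LUTS AE rate and gives no calculation for the Phase 2 size, so there is no figure to reproduce. The check sets the two parts of 7.1 against the same histories.

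| History of a symptom | General definition | Rules (a)-(c), literal |
|---|---|---|
| Present at baseline, continues past 72 hours, no worse than baseline | Not an AE | AE by (a) or (b) |
| Present at baseline, resolves, returns later at or below baseline severity | Not an AE | AE by (c) |
| New, or worse than baseline to a clinically significant degree, past 72 hours | AE | AE |

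The two texts agree on the third row and disagree on the first two.

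**Row 1, residual symptoms.** Inputs: entry IPSS of at least 15 (5.4); mild band 7 or less (14.8.1). The smallest fall that takes a subject entering at 15 into the mild band is 15 − 7 = 8 points, and at any score from 1 to 7 he still reports some symptoms. As an illustration, take a man who goes from 22 to 10. He has improved by 22 − 10 = 12 points, yet 14.8.1 still places him where "8-19 represents those with moderate symptoms". A clear responder can therefore meet (a) or (b) read literally.

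**Row 2, returning symptoms.** Each IPSS question is scored 0 to 5, with 0 meaning not at all (14.8.1). Let one item score b at baseline (1 to 5), fall to 0, and later return to r, with 0 < r ≤ b. The symptom resolved and recurred, so (c) applies. Because r does not exceed b, the general definition does not. The sentence in 7.1 that has recurring events reported separately points towards counting, although it presupposes that the first episode was an event.

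**Other sections.** Section 7.2 excludes only procedure-attributed symptoms lasting 72 hours or less that lead to no intervention or added hospital stay, so it does not reach either row. Section 7.2.1 shows the sponsor handling a similar problem explicitly: erectile dysfunction is common in this population, so only new cases attributable to the procedure within the first 3 months count. LUTS has no such limit.

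**Bounds on the count.** Assume 15 subjects treated and evaluable. Exact (Clopper-Pearson) 95% limits:

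- Literal (a)-(c), with residual symptoms in every subject: 15/15 = 100%; lower limit 0.025^(1/15) = 78.2%.
- General definition, with nobody worse than baseline: 0/15 = 0%; upper limit 1 − 0.025^(1/15) = 21.8%.
- General definition, with three worse than baseline: 3/15 = 20% (4.3% to 48.1%).

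The documents give no worsening rate. At assumed true rates of 5%, 10%, 20% and 30%, the expected counts under the general definition are 15 × rate = 0.75, 1.5, 3.0 and 4.5.

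**The case against.** The best reply is that the opening definition is stated for the whole protocol and governs what follows. On that reading (a)-(c) only set the timing for events that already qualify as adverse changes; they mirror the preceding sentence on LUTS that begins and ends within 72 hours. Rules (a) and (b) also speak of LUTS occurring, which suggests onset, and nothing has newly occurred in a man whose long-standing symptoms have improved. This is a reasonable reading and weakens the residual-symptom case. It does not remove the conflict: the LUTS rules are more specific, come later and are worded as mandatory, and no available text gives an order of precedence. Rule (c) does not rest on onset wording in the same way.

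Two further points stand. First, a low IPSS total does not prove resolution, since 7 or less is still labelled mild symptoms; rule (c) has to be argued symptom by symptom, as above. Second, loss of effect is already visible through IPSS change from baseline (Endpoint 4, 5.3.4), collected to year 5, so no extra listing is needed.

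A reader might infer that these events would be reported as device harm. The documents do not support that. AE status in 7.1 is independent of cause, 7.7 lets the investigator attribute an event to underlying disease, and 14.2 reports by relationship. The separation is imperfect, because the Definite category in 7.7 is worded on timing and does not require other causes to be excluded, but it exists.

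Figure 7-1, the AE determination flowchart, was not available and may state how baseline is handled.

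**Conclusion.** The point holds as an unreconciled conflict within 7.1. It would be wrong to say that the section lacks a baseline reference: the reference is there, but (a)-(c) neither repeat it nor defer to it. The conflict is clearest for BPH symptoms that return at or below baseline severity in later follow-up, and weaker for residual symptoms. Its consequence is that the LUTS AE frequency under 14.2 depends on which rule a site applies.

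The range 0/15 to 15/15 is a logical bound and should not be read as the expected spread. The upper end needs all 15 subjects to keep some symptoms and the literal rule to be applied throughout; the lower end needs nobody to worsen and the general rule to be applied throughout. The true gap cannot be estimated from the documents. No hypothesis test depends on it. It should be corrected because the LUTS count is part of the Phase 2 safety result and the correction is small. The conclusion assumes that Figure 7-1 does not already settle the matter.

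**What to change.** - **In 7.1,** state that (a), (b) and (c) apply to LUTS that is new or worse than the subject's documented baseline, judged against the baseline IPSS items or, for symptoms the questionnaire does not cover, the recorded history. Comparing items rather than totals still catches a new irritative symptom in a man whose total score has improved.
- **Symptoms at or below baseline.** Report persisting or returning BPH symptoms through the existing IPSS change-from-baseline endpoint.
- **Symptoms with an identified new cause,** such as stricture, infection or retention, remain AEs under that diagnosis, in line with the instruction in 7.1 to classify by underlying cause.
- **Check Figure 7-1** and align it with the amended text.

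The cost is one clause and brief site retraining; baseline IPSS and a LUTS form are already in use. There is one real downside: a late complication that first appears as LUTS no worse than baseline would not be counted until it is diagnosed. Stricture, listed as anticipated in 7.3, is an example. That risk is small, and the third item limits it.
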